### **Reminder Call 3 (Day 11 +/-2 days)**

- review sample collection instructions
- review time, date and location of Visit 3
- review memory aide with parent/guardian

### **Visit 3 (Day 14 +/- 4 days)**

- inclusion and exclusion criteria will be reviewed to determine if child still meets criteria for study (has not had any vaccines since Visit 1)
- submission of all remaining daily stool specimens collected from the infant
- memory aide reviewed with the parent and collected
- payment for time and travel provided for the study procedures
- ensure parent has written plan on how to receive next dose(s) of rotavirus vaccine
- administer parent/guardian satisfaction survey

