Recruitment and enrollment will occur prior to the first study visit. There will be three scheduled study visits after recruitment/enrollment. . Infants will be randomized to either RV1, RV1 plus other immunizations, RV5 alone, or RV5 plus other immunizations. Visit 1 (day 0) will include blood, saliva, stool and breast milk collection . The MRI and ultrasound will be performed prior to vaccination. Children will receive the immunizations to which they are randomized. Imaging personnel and parents will be blinded to rotavirus vaccine type; they will be informed about other vaccines administered. A second MRI and ultrasound will be performed at Visit 2 (day 5) and blood and stool samples collected. Parents will be unblinded at the completion of Visit 3 (day 14). Arrangements will be made to get remaining doses of same rotavirus vaccine. Daily stool samples will be collected at home during the 15 day study period (on vaccination day 0 and for next 14 days). A memory aid will be completed to collect reactogenicity data on days 0 and for the next 14 days. Remaining stools and reactogenicity data from parents will be collected at Visit 3. **See Appendix 1 for detailed description of visits and timeline.**

We will assess blood and stool cytokine responses and intestinal anatomy and motility after rotavirus vaccination by comparing pre-vaccination with post-vaccination responses in the study infants. Cytokines and intestinal anatomy and motility will be assessed at baseline (Visit 1, the day of vaccine receipt) and 5 days after vaccination (Visit 2). For both blood and stool, the following cytokines will be tested: IL-2, IL-6, IL-7, IL-8, IL-15, INF- $\gamma$  and TNF- $\alpha$ . Additional biomarkers may be studied. The 5 day period post-vaccination was chosen because this time period corresponds with the peak period for intestinal replication of rotavirus vaccine virus for both vaccines.

In order to protect the health of infants, we will provide procedures to facilitate and assure that infants enrolled in the study will receive the routinely recommended vaccines for 2 month old infants which are DTaP, Hib, PCV13, HBV and IPV that will also allow them to get their 4 month vaccines on schedule.

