### 6.4 Stool Collection

Parents will be asked to collect bulk stool samples daily (Day 0-Day 14) to assess rotavirus vaccine virus shedding patterns and stool cytokines. Cytokines will be tested for stools from Visit 1 and Visit 2 (stool collected on the days of the MRI). Vaccine virus shedding (qualitative) will be done on stools from Visit 1 through Visit 2 (stool collected on the day of the MRI). If the Visit 2 stool is positive then the additional stools will be tested to determine the duration of shedding. If the Visit 2 stool is positive, a quantitative PCR will be done on that stool.

Only bulk specimens will be collected. Stools may be collected in diapers and placed in collection bag. Rectal swabs will not be used for stool collection because we have found that they are not a reliable source for detection of rotavirus. Specimens will be refrigerated or frozen within 8 hours of collection. Parents who collect the specimen at home will be asked to freeze the specimen within 8 hours of collection. Once delivered to the lab, bulk stool and extracts will be frozen at a minimum of -20°C.

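### The Visit 3 window opens on Day 10, so an on-time visit can end stool and reactogenicity collection up to four days before the planned Day 14

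*Combined protocol and SAP*

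**What the plan says.** The collection period runs to Day 14 for both data streams. For stools, Section 4.1 states: "Daily stool samples will be collected at home during the 15 day study period (on vaccination day 0 and for next 14 days". Section 6.4 agrees: "Parents will be asked to collect bulk stool samples daily (Day 0-Day 14". For reactogenicity, Section 4.1 states: "A memory aid will be completed to collect reactogenicity data on days 0 and for the next 14 days". Section 6.8 and the Appendix 1 grid show the same period.

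Visit 3 is where this material comes in. Section 4.1: "Remaining stools and reactogenicity data from parents will be collected at Visit 3". The Visit 3 list in Section 5.3 has "submission of all remaining daily stool specimens collected from the infant" and "memory aide reviewed with the parent and collected". Sections 4.1 and 10.1 both place the unblinding of parents at the completion of Visit 3.

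Sections 4.1 and 6.9 and Appendix 1 put Visit 3 on Day 14. Section 5.3 alone gives a tolerance: "Visit 3 (Day 14 +/- 4 days". The call meant to precede the visit is "Reminder Call 3 (Day 11 +/-2 days".

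**The concern.** A visit on Day 10, 11, 12 or 13 follows the protocol, but it takes back the diary and the last stools before the planned collection has ended. Section 3.4 justifies the 14-day period on the grounds that most vaccine-associated events fall within it and shedding becomes less frequent afterwards. The lost days are therefore inside the protocol's own period of interest.

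Three things are at stake:

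- **Shedding duration.** For an infant still shedding at an early visit, the observed duration is cut off on a day set by scheduling. Section 10.3 has no method for truncated durations.
- **14-day reactogenicity.** Infants would be observed for different lengths of time, and nothing in the plan identifies those with short follow-up.
- **Feasibility, a primary objective.** Appendix 2 sets 70% benchmarks for stools, temperature recording and reactogenicity. An early visit uses up most or all of the missed days these allow. The same infant counts as on time under the study-visit benchmark, so a scheduling effect could be read as poor parental compliance.

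**Working it through.** **Inputs.** Collection period Day 0 to Day 14 (Sections 4.1, 6.4, 6.8). Visit 3 tolerance of 4 days either side of Day 14 and Reminder Call 3 tolerance of 2 days either side of Day 11 (Section 5.3). Benchmarks of 70% of 14 stools, 70% of study days for temperature and 70% of days for reactogenicity (Appendix 2).

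**Plan's own figure.** Days 0 to 14 inclusive: 14 − 0 + 1 = 15, which matches the 15-day study period in Section 4.1.

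**Visit window.** 14 − 4 = Day 10 to 14 + 4 = Day 18, nine days.

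**Days lost.** For a visit on Day v, the loss is 14 − v if v < 14, and otherwise 0.

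| Visit 3 day | Days not reached | Lost of 15 | Most in hand |
|---|---|---|---|
| 10 | 11–14 | 4 (26.7%) | 11 |
| 11 | 12–14 | 3 (20.0%) | 12 |
| 12 | 13–14 | 2 (13.3%) | 13 |
| 13 | 14 | 1 (6.7%) | 14 |
| 14–18 | none | 0 | 15 |

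The last column assumes that the visit day's own stool and diary entry are complete by the time of the visit. All of the loss comes from the early half of the window.

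**Benchmarks after a Day 10 visit.** The documents do not settle whether Day 0 counts, or whether the diary denominator is 14 or 15 (Section 4.1 collects Days 0–14; the grading text in Section 6.8 refers to Days 1–14).

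- Stools: 0.70 × 14 = 9.8, so 10 are needed. Days 1–10 supply 10 (no miss allowed). With Day 0 counted there are 11 (one miss allowed).
- Diary and temperature over 15 days: 0.70 × 15 = 10.5, so 11 are needed and 11 exist (no miss allowed).
- Diary and temperature over 14 days: 10 are needed. Days 1–10 supply 10 (no miss allowed), or 11 with Day 0 counted (one miss allowed).

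The margin is therefore zero or one missed day. After a visit on Day 14 or later it is four or five (14 − 10 = 4; 15 − 11 = 4; 15 − 10 = 5 with Day 0 counted against 14). A parent who misses nothing still passes after a Day 10 visit (10/14 = 71.4%; 11/15 = 73.3%), and the benchmark then does not show the four lost days.

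**Order of contacts.** Reminder Call 3 spans 11 − 2 = Day 9 to 11 + 2 = Day 13, so it can fall after a Day 10 visit.

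**Recovery.** No section read provides for collection after Visit 3, or for holding back unblinding, in infants still in the study. The separate contact at 14 days in Section 4.4 concerns withdrawn subjects.

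**The case against.** The best defence is that Day 14 is plainly the target and the tolerance is ordinary scheduling latitude, so most visits may fall late enough to lose little or nothing. The frequency is indeed unknown, and the loss per infant is 0 to 4 days. But the wording makes an early visit compliant, and nothing in it tells site staff to avoid one.

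A second defence is that the affected outcomes are exploratory and largely descriptive. This stands. A reader might infer that the primary result is at risk. It is not: ileum thickness is measured on the MRI at Visit 2 (Day 5, give or take one day), and radiologists stay blinded until study completion. The planned shedding–imaging correlation uses a sample taken near the imaging, so it is untouched too. Section 10.3 names no specific analysis of shedding duration.

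A reader might also infer that unblinding biases the late reactogenicity reports. That holds only if Day 11–14 reports are gathered after an early visit. On the procedures described they would simply be absent. Parents are in any case blinded only to RV1 versus RV5, not to whether routine vaccines were given.

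It is tempting to say that a Day 10 infant can meet the benchmarks only with no missed day at all. That depends on counting rules the documents leave open; on some of them one miss is allowed.

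Finally, Section 5.3 refers to written parent instructions for Visit 3 (Appendix 7) that are not in the text read here. The statement that nothing recovers the lost days is limited accordingly.

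**Conclusion.** The point holds as an avoidable inconsistency of moderate weight. The Visit 3 window conflicts with the Day 0–14 collection period, and a compliant early visit costs 1 to 4 of 15 days (6.7% to 26.7%). It truncates exploratory shedding-duration and reactogenicity data and leaves zero or one missed day under the 70% collection benchmarks after a Day 10 visit.

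The size across the trial cannot be computed, for two reasons. The distribution of visit days is not given. In addition, Section 6.4 tests stools after Visit 2 only when the Visit 2 stool is positive, while Sections 3.4 and 8.2 have all collected stools tested, so the share of infants whose late stools matter for shedding duration is unsettled. The conclusion assumes that Visit 3 is the last collection point, as the body text describes.

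**What to change.** Set the Visit 3 window so that it does not open before Day 14, for example Day 14 to Day 18. This permits no visit later than now allowed. State that the memory aid is collected, and parents are told the vaccine type, only once the Day 14 stool and diary entries are in hand. Provide for later hand-in when the visit falls during Day 14, because that day's entry may not yet be complete.

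Reminder Call 3 (Day 9 to Day 13) then always precedes the visit and needs no change. In Appendix 2, state whether Day 0 counts and which denominator applies to the diary and temperature benchmarks.

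Keeping the present window and arranging hand-in after early visits could also recover the data, but unblinding would still have to wait and an extra collection step would be needed.

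The cost is protocol wording and a scheduling window of five days instead of nine (Days 14–18 against Days 10–18). The narrower window makes the benchmark of 70% of subjects completing all visits on time somewhat harder to meet, which should be accepted openly because feasibility is a primary objective.

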## 6 STUDY PROCEDURES

### 6.1 Rotavirus Vaccine Randomization and Administration

Infants will be randomized to receive 1) RV1 alone, 2) RV5 alone, 3) RV1 with routine immunizations (DTaP, Hib, PCV13, HBV and IPV or 4) RV5 with routine immunizations prior to Visit 1. They will receive the vaccination(s) after the MRI/Ultrasound is completed at Visit 1.

### 6.2 Breast Milk Collection

Breastfeeding mothers will be asked to collect one breast milk sample to bring to Visit 1 to assess anti-rotavirus IgA antibody ELISA and the secretor status of the mother. Approximately 30 mL of breast milk will be collected at home prior to the study visit. Collection via hand expression or breast pump is acceptable. The breast milk sample should be collected up to 24 hours prior to the clinic visit and stored and transported with an ice pack. Once delivered to the lab, the whey will be separated from the sample, and the breast milk will be frozen at a minimum of -20°C. If unable to collect this sample at Visit 1, it can be collected at Visit 2 or 3.

### 6.3 Saliva Collection

At Visit 1, a saliva specimen will be collected for secretor genotyping by placing sterile cotton-tipped swabs in the infant's mouth, saturating it with saliva and placing it in the Oragene (DNA Genotek) solution. Once mixed with Oragene, the DNA in saliva is stabilized and can be stored indefinitely at room temperature. If unable to collect this sample at Visit 1, it can be collected at Visit 2 or 3.

### 6.4 Stool Collection

Parents will be asked to collect bulk stool samples daily (Day 0-Day 14) to assess rotavirus vaccine virus shedding patterns and stool cytokines. Cytokines will be tested for stools from Visit 1 and Visit 2 (stool collected on the days of the MRI). Vaccine virus shedding (qualitative) will be done on stools from Visit 1 through Visit 2 (stool collected on the day of the MRI). If the Visit 2 stool is positive then the additional stools will be tested to determine the duration of shedding. If the Visit 2 stool is positive, a quantitative PCR will be done on that stool.

Only bulk specimens will be collected. Stools may be collected in diapers and placed in collection bag. Rectal swabs will not be used for stool collection because we have found that they are not a reliable source for detection of rotavirus. Specimens will be refrigerated or frozen within 8 hours of collection. Parents who collect the specimen at home will be asked to freeze the specimen within 8 hours of collection. Once delivered to the lab, bulk stool and extracts will be frozen at a minimum of -20°C.

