### **Rotavirus Vaccine Virus Shedding**

We will use RT-PCR to identify rotavirus vaccine strains, to examine the duration of shedding and to quantitate rotavirus shedding 5 days post-vaccination. We will then assess the correlation of the amount of virus shedding with intestinal anatomy and motility as well as cytokine and inflammatory responses. The Ct values will be examined and categorized as none, low or high for analysis. We chose 14 days to assess the duration of shedding since studies have shown that most vaccine-associated events occur in the first 14 days and shedding becomes less frequent after 14 days. Vaccine virus shedding (qualitative) will be done on all stools collected. In addition, since we will be collecting reactogenicity data for Days 0-14, stool from other days could be evaluated for stool cytokines should the infant have an adverse event either before or beyond the Visit 2 stool evaluation.

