### **Visit 2 (Day 5 +/- 1 day) Post-Vaccination)**

- contact information will be reviewed and updated if necessary
- inclusion and exclusion criteria will be reviewed to determine if child still meets criteria for study (no vaccines given since last visit)
- MRI to assess intestinal anatomy and motility
- ultrasound to assess intestinal anatomy
- submission of daily stool specimens collected
- blood collected for cytokine testing
- memory aide will be reviewed with the parent and the parent will demonstrate ability to take temperature and will be instructed in the collection of reactogenicity, adverse event, fever and concomitant medication administration data for remaining study period
- distribution of supplies for daily stool collection with instructions for storage and return
- payment for time and travel for study procedures
- written instructions (Appendix 7) given to the parent with the date, time and location for Visit 3 and need to return with the collected daily stool specimens and memory aide
- study personnel will complete the Case Report Form (CRF)

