## 8.2 Stool-RV1 and RV5 Shedding and Cytokine Responses

Stool specimens will be utilized for both assessment of rotavirus vaccine shedding patterns and measurement of stool cytokines. For stool cytokine testing, stool specimens from Visit 1 and Visit 2 will be used. For assessment of rotavirus vaccine virus shedding patterns, all collected stools will be analyzed. Cytokine testing will be done on Visit 1 and Visit 2 specimens only. All stool samples will be kept frozen at -20 °C or colder until testing. For determination of rotavirus shedding and cytokine responses, stools will be thawed and nucleic acids will be extracted. For cytokine determination, PCR will be performed using Taqman gene expression assays from Life Technology for each of the cytokines of interest. The following cytokines will be done: IL-2, IL-6, IL-7, IL-8, IL-15, INF- $\gamma$  and TNF- $\alpha$ . Additional biomarkers or cytokines may be done should funding become available.

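### Sections 3.4 and 8.2 test every collected stool for vaccine virus, but Section 6.4 tests stools after Visit 2 only if the Visit 2 stool is positive, so under 6.4 the 14-day duration window depends on the shedding result

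*Combined protocol and SAP*

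**What the plan says.** Three sections of the protocol set the stool-testing rule.

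- Section 3.4 (Rotavirus Vaccine Virus Shedding): "Vaccine virus shedding (qualitative) will be done on all stools collected". On the window it says "We chose 14 days to assess the duration of shedding", giving as one reason that "shedding becomes less frequent after 14 days".
- Section 8.2: "For assessment of rotavirus vaccine virus shedding patterns, all collected stools will be analyzed".
- Section 6.4: "Vaccine virus shedding (qualitative) will be done on stools from Visit 1 through Visit 2", and then "If the Visit 2 stool is positive then the additional stools will be tested to determine the duration of shedding". Quantitative PCR is run on the Visit 2 stool if it is positive.

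Section 4.1 fixes the collection period: "Daily stool samples will be collected at home during the 15 day study period", that is, Day 0 to Day 14. Section 5.3 gives the timing of the second imaging visit as "Visit 2 (Day 5 +/- 1 day) Post-Vaccination", so Visit 2 can fall on Day 4, 5 or 6.

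Exploratory objective 3 (Section 3.3) concerns the pattern and level of shedding after each vaccine. Section 10.3(a) provides generic descriptive statistics for fecal variables. Section 10.3 does not name duration of shedding as a variable and gives no rule for deriving it.

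**The concern.** Sections 3.4 and 8.2 are unconditional and 6.4 is conditional. A laboratory cannot obey both for an infant whose Visit 2 stool is negative, and no passage says which rule takes precedence.

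The difference affects the data. Under 6.4, whether an infant is observed beyond Visit 2 depends on that infant's own shedding result. Visit 2-positive infants are followed to the end of collection; the rest are followed only to Visit 2. An infant who sheds intermittently and happens to be negative at Visit 2, or who first sheds after Visit 2, is recorded as having stopped or as never having shed. If the proportion positive at Visit 2 differs between RV1 and RV5, observation time differs by vaccine as well, and a comparison of duration would mix true duration with length of observation.

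The choice of 14 days in 3.4, and its remark on what happens after Day 14, imply that some shedding is expected well past Visit 2.

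**Working it through.** The plan states no figure on this point, so there is nothing to reproduce. The check compares the testing rules and counts stool-days.

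**Inputs.** Collection runs Day 0-14, which is 15 stool-days, 14 of them after vaccination (4.1, 6.4). Visit 2 is on day V = 4, 5 or 6 (5.3). Enrolment is up to 150 infants (4.1). The counts assume a stool every day through Day 14.

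**Stool-days untested in a Visit 2-negative infant under 6.4** = 14 - V:

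| Visit 2 day | Untested | Share of 15 | Share of 14 post-vaccination days | Latest recordable positive (V - 1) |
|---|---|---|---|---|
| 4 | 10 | 67% | 71% | Day 3 |
| 5 | 9 | 60% | 64% | Day 4 |
| 6 | 8 | 53% | 57% | Day 5 |

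Under 3.4 and 8.2 the untested count is 0 for every infant.

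**Error in the last positive day**, for a Visit 2-negative infant with any later positive stool:

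- The earliest possible later positive is Day V + 1 and the latest recordable one is Day V - 1, so the understatement is at least (V + 1) - (V - 1) = 2 days.
- If the Day 14 stool is positive, it is at least 14 - 3 = 11, 14 - 4 = 10 or 14 - 5 = 9 days.
- With no positive before Visit 2, the infant is recorded as a non-shedder.
- For an infant who had truly stopped before Visit 2, the error is zero.

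**Illustration on assumed inputs.** Suppose an infant sheds through Day L, each daily stool is independently positive with probability d, and Visit 2 is on Day 5. The chance that shedding after Visit 2 is missed is (1 - d) × [1 - (1 - d)^(L - 5)].

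- d = 0.9, L = 7: 0.1 × (1 - 0.1²) = 0.099.
- d = 0.7, L = 7: 0.3 × (1 - 0.3²) = 0.273.
- d = 0.5, L = 7: 0.5 × (1 - 0.5²) = 0.375.

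With L = 14 the values are 0.100, 0.300 and 0.499. The documents give neither d nor L. The range shows only that the loss could be small or large.

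**What is not affected.** The shedding-imaging correlation in 10.3(b) uses the sample taken close to imaging, which is tested under either rule. The quantitative PCR in 6.4 agrees with 3.4, which quantifies shedding 5 days after vaccination.

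**The case against.** The strongest reply is that the harm is conditional. Two of the three sections already state the all-stools rule, so what is certain is an inconsistency in the text; truncation follows only if the laboratory works from 6.4. That is correct. But 6.4 is the procedures section and the most specific of the three, so it may well be the one followed.

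Second, 6.4 has an intelligible rationale. Section 4.1 places Day 5 at the peak of vaccine-virus replication for both vaccines, so testing later stools only when the peak-time stool is positive is a reasonable economy. It loses nothing if shedding starts by Visit 2 and is continuous. The documents do not state that assumption. Nor do they say that intermittent or late shedding follows a negative Visit 2 stool; the plan leaves the question open, and the 6.4 rule would prevent the data from answering it.

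Third, this is an unpowered pilot, shedding is exploratory, and no duration comparison or censoring method is specified. This limits the weight of the point but does not remove the contradiction.

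Fourth, Visit 3 may fall as early as Day 10 (Section 5.3). If collection stopped then, the untested days would be 6, 5 or 4 instead of 10, 9 or 8. The counts above are therefore upper figures.

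**Conclusion.** The concern holds. Sections 3.4 and 8.2 conflict with 6.4, and following 6.4 makes the duration window depend on the outcome it is meant to measure. In a Visit 2-negative infant, 10, 9 or 8 of 15 stool-days go untested, given daily stools to Day 14, and any later positive leads to an understatement of at least 2 days in the last positive day. The size of any average bias, or of any RV1 versus RV5 difference in it, cannot be derived from the documents.

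The consequence is limited to exploratory summaries of shedding pattern and duration. The primary ileum-thickness analysis and the shedding-imaging correlation stand. Because stools are collected and frozen regardless of the Visit 2 result, the loss can be recovered if the rule is settled while the samples remain usable. This should be corrected before shedding results are analysed.

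**What to change.** Reconcile Sections 3.4, 6.4 and 8.2.

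**Preferred.** Delete the conditional in 6.4 and test all collected Day 0-14 stools qualitatively in every infant, as 3.4 and 8.2 already state. Keep quantitative PCR for positive Visit 2 stools. This also removes a gap: 6.4 has no rule for a missing Visit 2 stool.

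The cost is wording plus assays that two sections already promise. If all 150 infants were Visit 2-negative with every stool collected, the extra assays would be 150 × 10, 9 or 8 = 1,500, 1,350 or 1,200, so the ceiling is 1,500. If 70% of those stools were collected, the figures would be 1,050, 945 or 840. The 70% is a scenario using the level named in Appendix 2, whose benchmark applies it per parent and only to 70% of parents. Each Visit 2-positive infant lowers these figures, because 6.4 already tests that infant's later stools.

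**If those assays will not be run.** Amend 3.4 and 8.2 instead. Define the measure as shedding through Visit 2 for all infants, record later untested stools as not tested, and make no 14-day duration comparison between RV1 and RV5. Later results from Visit 2-positive infants could still be described, labelled as conditional on that positive stool. This costs wording only, but gives up the 14-day duration measure.

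Under neither option should Visit 2-negative infants be treated as right-censored at Visit 2. Their observation ends because the stool was negative, so the censoring would be informative.

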## **4 Research Plan**

### **4.1 Overview of Study**

This study is a prospective clinical study designed to 1) examine the effects of RV1 and RV5 alone or with other routine immunizations on gastrointestinal anatomy 2) to assess the feasibility of conducting a larger scale study. Exploratory objectives include 1) to examine the effects of RV1 and RV5 with or without other routine immunizations on gastrointestinal motility 2) to examine the effects of RV1 and RV5 with or without other routine immunizations on blood and stool cytokines and inflammatory responses, including clinical reactogenicity events 3) to assess patterns and level of vaccine virus shedding after RV1 and RV5 4) to provide preliminary data assessing associations with the pattern of rotavirus vaccine strain (RV1 and RV5) shedding in the stool and blood, stool cytokine responses, and the anatomy and/or functional motility of the small intestine; and examine other factors such as maternal antibody, breast milk antibody, and human blood group antigens to see if these factors modify these responses and 5) to compare MRI and ultrasound imaging.

Healthy infants 6-13 weeks of age will be randomized (1:1:1:1) to receive either, RV1 alone, RV5 alone, RV1 with ACIP routinely recommended immunizations (Diphtheria, Tetanus and Pertussis (DTaP), *Haemophilus influenzae* type b (Hib), pneumococcal conjugate (PCV13), Hepatitis B (HBV) and

inactivated polio (IPV)) or RV5 with routine immunizations. Imaging study personnel and parents will be blinded to the rotavirus vaccine type; parents will be informed about the rotavirus vaccine type at the completion of the study. Up to 150 infants will be enrolled (see inclusion/exclusion below). The age-group of infants 6-13 weeks of age was chosen so enrolled infants can receive their first dose of rotavirus vaccine at the AAP/ACIP recommended age of 2 months (minimum age of 6 weeks and maximum age of 14 weeks and 6 days) and, to assure that other ACIP recommended vaccines can be administered at the recommended age.

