To assess how vaccine shedding is related with the primary outcome by looking at the correlation between the imaging outcome and the fecal shedding for each group (using sample obtained close in time with the imaging). This will be examined using Pearson or Spearman correlation coefficients based on the normality of the data. The resulting correlation coefficient from each group can be compared with each other (pairwise) using Fisher's transformation and compare the resulting z-scores. If the correlation are not different we may then combine the groups and run the correlation across group to get an insight on the relationship between shedding and imaging parameter.

For all the other imaging parameters (cecum thickness, wave pattern and amplitude) similar analysis described for the primary outcome (ileum thickness) will be conducted. For Lymph node presence a logistic regression instead of GLM, and for the lymph node number, and wave frequency a Poisson regression will be used.

For the cytokines outcome (IL2, IL6, IL7, IL8, IL15, TNF) similar analysis described for the primary imaging outcome including examination of modifying variables and potential subsequent stratified analysis will be conducted.

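### The shedding variable in the shedding–imaging correlation is not defined, and the coding named in Section 3.4 coarsens the Ct values at cut-points that are not fixed in advance

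*Combined protocol and SAP*

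**What the plan says.** Three sections of the combined protocol and SAP bear on this.

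- **Section 6.4 (Stool Collection)** sets out who is tested: "Vaccine virus shedding (qualitative) will be done on stools from Visit 1 through Visit 2 (stool collected on the day of the MRI". It then says: "If the Visit 2 stool is positive, a quantitative PCR will be done on that stool". Every infant with a Visit 2 stool therefore has a positive or negative result, and the positives also have a quantity.
- **Section 3.4 (Rotavirus Vaccine Virus Shedding)** gives the aim: "We will then assess the correlation of the amount of virus shedding with intestinal anatomy and motility as well as cytokine and inflammatory responses". The next sentence gives the coding: "The Ct values will be examined and categorized as none, low or high for analysis". No Ct cut-points appear there or elsewhere.
- **Section 10.3(b) (Inferential statistics)** describes "looking at the correlation between the imaging outcome and the fecal shedding for each group (using sample obtained close in time with the imaging", and continues: "This will be examined using Pearson or Spearman correlation coefficients based on the normality of the data". The group coefficients may then be compared in pairs by Fisher's transformation and pooled if they do not differ. It does not say whether shedding means a Ct value, a quantity or the three-level category. It does not cross-refer to Section 3.4 and gives no value for a negative stool.

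**The concern.** Three choices are left to the analyst.

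1. **Scale.** Choosing between Pearson and Spearman on normality presumes a continuous variable. Section 3.4 names a three-level one. The normality check in Section 10.3(a) is also written for continuous outcomes, fecal ones included.
2. **Cut-points.** Section 3.4 has the Ct values examined and then categorized, with no boundary between low and high stated. The boundary can therefore be chosen after the distribution, and possibly its relation to imaging, has been seen.
3. **Negatives.** The natural reading is that a negative Visit 2 stool is coded as none, but no section says so. Nor does any section say what happens to an infant who was positive earlier and negative at Visit 2.

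The hypothesis in Section 3.2 includes a relationship between the pattern of shedding and bowel anatomy or motility, and exploratory objective 4 takes it up. All four arms receive a rotavirus vaccine, so shedding against imaging change is one of the few within-trial looks at a dose-response relationship. The plan also intends to report effect sizes to support later studies, and an effect size on an undefined scale is hard to carry forward.

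**Working it through.** **No figure to reproduce.** The Power paragraph of Section 10.3 says no power calculation was done, and no effect size is given for this correlation.

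**Inputs from the documents**
- Section 4.1: "Up to 150 infants will be enrolled", allocated 1:1:1:1. 150 / 4 = 37.5, so about 37 per arm.
- Feasibility benchmark (Appendix 2): at least 70% complete both MRIs. 0.7 × 37 = 25.9, about 26 per arm; 0.7 × 150 = 105 in all.

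**Assumptions not in the documents**
- Two-sided 5% level.
- Latent log shedding and thickness change bivariate normal, with true correlation 0.4 per arm or 0.3 pooled.
- Share positive at Visit 2 between 20% and 80%.
- Low/high cut at the median of positives.

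**Scale of the problem.** The smallest correlation with 80% power is tanh[(1.96 + 0.84) / √(n − 3)].
- n = 37: tanh(2.80 / √34) = 0.45
- n = 26: tanh(2.80 / √23) = 0.53

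A within-arm correlation of 0.4 is thus below what one arm can reliably detect under any coding.

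**Comparison of codings.** In each replicate an infant is negative when latent shedding falls below a detection threshold. Both codings are applied to the same data and tested by Spearman. The figures below use 4,000 replicates at n = 37 and 2,500 at n = 26, with true correlation 0.4.

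| n | Share positive | Ct kept, negatives tied lowest | None/low/high | Difference (points) |
|---|---|---|---|---|
| 37 | 20% | 39.5% | 39.0% | 0.5 |
| 37 | 50% | 57.5% | 55.5% | 2.0 |
| 37 | 80% | 65.0% | 59.2% | 5.8 |
| 26 | 20% | 26.6% | 26.6% | 0.0 |
| 26 | 50% | 42.1% | 40.9% | 1.2 |
| 26 | 80% | 47.9% | 42.1% | 5.8 |

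A second set, with 3,000 replicates per scenario and 40% to 80% positive, gave:
- n = 37, correlation 0.4: 52–63% against 51–56%
- n = 26, correlation 0.4: 40–49% against 39–43%
- n = 105, correlation 0.3: 73–83% against 72–77%

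The largest difference at matching ends of these ranges is 63 − 56 = 7 points. The Monte Carlo standard error of a single power figure is at most 0.5 / √2,500 = 1.0 point. The loss grows with the share positive, because more infants then have a Ct value to coarsen.

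**Choice of coefficient.** For the three-level variable at n = 37, Pearson had 40.8%, 57.6% and 61.5% power at 20%, 50% and 80% positive, against 39.0%, 55.5% and 59.2% for Spearman. The misfit between a normality rule and a three-level variable is a defect of specification. It does not cost power.

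**The case against.** The strongest reply is that the sections form one sequence: qualitative test, quantitative PCR if positive, then Ct grouped with a none level for the rest. Quantifying only positives is normal, since a negative stool has no quantity. That stands.

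A reader might go further and infer that the correlation would leave out non-shedders, because only positives have a quantitative result. The documents do not support this. Section 6.4 gives infants with a negative Visit 2 stool a qualitative result, Section 3.4 has a category for them, and nothing excludes them. Nor must the analyst choose between dropping negatives and discarding Ct, since a rank correlation with negatives tied lowest does neither. A positives-only run would be expensive (7%, 15% and 36% power at n = 37 for 20%, 50% and 80% positive), but that is only a warning against a complete-case run on the quantitative PCR field. It does not measure a fault in the plan.

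It can also be said that the plan's own rule reaches Spearman anyway, since a three-level variable will almost always fail Shapiro-Wilk. In a simulation check it failed in at least 99.7% of replicates. That is fair as to the method reached, but it leaves the scale, the negatives and the cut-points undefined.

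Finally, the analysis is exploratory, in a pilot without power calculations. That limits the priority and is accepted.

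**Conclusion.** The point holds in a limited form. Section 10.3 does not name the shedding variable or the coding of negatives. Section 3.4, if followed, coarsens Ct among positives at boundaries not fixed beforehand. The power lost is about 0 to 7 percentage points, for 26 to 37 infants per arm at a true correlation of 0.4 or 105 infants at 0.3. That range depends on the assumed correlations, the assumed share positive and a median cut; none of these comes from the documents. A cut far from the median would change it.

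The stronger reason to act is that an avoidable choice made after seeing the data can be removed at no cost. This is a low-to-moderate priority improvement to an exploratory analysis (objective 4). It does not touch the primary comparison of ileum thickness.

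**What to change.** In Section 10.3(b):

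- Define shedding as Visit 2 viral load on its continuous scale (reversed Ct), with PCR-negative Visit 2 stools at the lowest tied rank. State that this coding applies whatever the earlier stools showed.
- Use Spearman within each group, in all infants who have a Visit 2 stool result and the imaging measure. Then pool as the section already describes.
- Keep none/low/high as a descriptive summary, with the Ct cut-points written down before any shedding data are examined. Cross-refer Section 3.4 to this definition.
- Report the share of positive stools beside each group coefficient. Section 10.3 says "The resulting correlation coefficient from each group can be compared with each other (pairwise) using Fisher's transformation", and heavy ties pull a coefficient down. With the same true correlation of 0.4 at n = 37, the mean coefficient was 0.27 at 20% positive and 0.37 at 80%, so groups can differ for that reason alone.

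The cost is analysis-plan wording. The testing in Section 6.4 already yields every value needed, so no assay, sample or visit is added.
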